The score developed by Demirjian et al has a good predictive ability for moderate to severe AKI after cardiac surgery in the European population.

4. Objectives

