4.1 Main

- Confirm the usefulness and externally validate the scale.
- Compare this scale with other models of AKI prediction after cardiac surgery: Thakar, Mehta, ISR, Callejas, Leicester, CRATE.

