Serum potassium (mmol/L)
Serum chlorine (mmol/L)
Serum bicarbonate (mmol/L)
Lactate (mmol/L)

Urgent re-intervention first 24h

YES/NO

Length of hospital stay (days)

Discharge status

Discharge

Éxitus

Need for dialysis at discharge

YES/NO

Postoperative renal failure

Creatinine at ICU admission

Creatinine at 24h

Creatinine at 48h

Creatinine at 72h

Peak creatine 4th to 7th day

Peak creatine 7th to 14th day

Last creatinine at hospital discharge

Does the patient develops Stage 1 AKI in the first 14 days?

*Stage 1 AKI: (\uparrow) Creatinine 1.5-1.9 times baseline or ≥ 0.3 mg/dL increase

If yes, which day?

Does the patient develops Stage 2 AKI in the first 14 days?

*Stage 2 AKI: (\uparrow) Creatinine 2-2.9 times baseline

If yes, which day?

Does the patient develops severe AKI in the first 14 days?

* Stage 3 AKI : (\uparrow) Creatinine ≥ 3 times baseline or ≥ 4 mg/dL increase or dialysis.

If yes, which day?

Does the patient requires renal replacement therapy within the first 14 days?

If yes, which day?

5.7 Sample size estimation: Taking into account an incidence of moderate severe AKI in Spain of 9% according to previous studies and using the

Wilcoxon test, 1045 patients are needed to detect a difference of 0.1 in aROC with a power of 80% and an alpha error of 0.05. Assuming a 10% loss to follow-up, 1150 patients would be needed.

5.8 Data collection: a data collection notebook will be used to carry out the study. The researcher will include in it the sample of patients, without any data that would allow their identification.

5.9 Analysis of results: the results will be analysed using the statistical package IBM-SPSS 20.0 for Mac OS and RStudio version 1.1.463. The basic statistics of centralisation and dispersion will be used to describe the results. For comparison of means, t-tests for independent data or Mann-Whitney U-tests will be used in those cases where the conditions for their application are violated. Chi-square tests shall be used for comparison of proportions. Bonferroni correction shall be applied for multiple contrasts. To study the predictive ability, 2 measures will be studied, the discrimination ability by means of the area under the ROC curve and the calibration by means of the Hosmer Lemeshow Test. The areas under the ROC curve will be compared using the Mann-Whitney U test.

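### 1150 enrolled leaves 1035 after a 10% loss, not the 1045 needed (very small effect); and sections 5.7 and 5.9 do not say whether the stated 80% power at 0.05 applies to the six score comparisons

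*Combined protocol and SAP*

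**What the plan says.** All references are to the combined protocol and SAP.

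- **Section 5.7 (sample size).** From a 9% incidence of moderate to severe AKI and a Wilcoxon test, "1045 patients are needed to detect a difference of 0.1 in aROC with a power of 80% and an alpha error of 0.05". It then adds: "Assuming a 10% loss to follow-up, 1150 patients would be needed". It does not give the AUC values behind the 0.1, any correlation between scores, or whether alpha is one- or two-sided.
- **Section 3 (hypothesis).** The score under study "has a good predictive ability for moderate to severe AKI after cardiac surgery in the European population". No comparator is mentioned.
- **Section 4.1 (main objectives).** There are two: "Confirm the usefulness and externally validate the scale", and "Compare this scale with other models of AKI prediction after cardiac surgery". The second lists six models: Thakar, Mehta, ISR, Callejas, Leicester and CRATE.
- **Section 5.9 (analysis).** After the tests for means and proportions it says: "Bonferroni correction shall be applied for multiple contrasts". It then turns to discrimination and calibration and ends: "The areas under the ROC curve will be compared using the Mann-Whitney U test". It gives no alpha for the AUC comparisons, no number of contrasts, and no confidence intervals for AUC differences.

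**The concern.** There are two separate matters, held with different confidence.

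**(a) The allowance for loss.** Multiplying the required number by 1.10 does not protect against losing 10% of those enrolled. The loss is taken from the larger number, so the plan's own target falls short of its own requirement. This is certain but minor.

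**(b) What the 80% refers to.** One power figure, at an unadjusted 0.05, stands beside a main objective with six comparisons and a general instruction to apply Bonferroni. Two things are left open: which difference was sized, and whether the correction reaches the AUC comparisons. A reader could take 80% as the power of each of the six comparisons as they will finally be tested, and then read a non-significant result as evidence that two scores perform alike. Whether 80% is the right figure depends on answers that the plan does not give.

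The test named for the AUC comparisons adds to this. The Mann-Whitney U test is for independent samples, whereas all the scores are computed on the same patients.

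**Working it through.** **Inputs from 5.7:** 1045 needed, 1150 enrolled, 10% loss, 80% power, alpha 0.05, AUC difference 0.1. **From 4.1:** six comparators. **Assumed:** a normal approximation; 1045 gives exactly 80% power; alpha is two-sided unless noted; and, in part (b), the Bonferroni family is these six comparisons.

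**(a) Loss to follow-up**

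1. The plan's figure reproduces: 1045 x 1.10 = 1149.5, rounded up to 1150.
2. Evaluable after a 10% loss: 1150 x 0.90 = 1035, which is 10 below 1045.
3. Loss that 1150 does cover: (1150 - 1045)/1150 = 9.1%.
4. Number that covers a 10% loss: 1045/0.90 = 1161.1, rounded up to 1162, which is 12 more than 1150.
5. Power at 1035: the noncentrality at 1045 is 1.960 + 0.842 = 2.802. At 1035 it is 2.802 x sqrt(1035/1045) = 2.788. Power = Phi(2.788 - 1.960) = 0.796.

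**(b) Power under each reading**

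The 1045 itself cannot be reproduced uniquely, because the AUCs, the correlation and the sidedness are not stated. The steps below therefore take the stated 80% at 0.05 as given.

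*Bonferroni covers the six comparisons, and 5.7 sized a score-versus-score difference:*

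1. Alpha per comparison: 0.05/6 = 0.0083, two-sided critical value 2.638.
2. Power at 1045: Phi(2.802 - 2.638) = 0.565. At 1035: Phi(2.788 - 2.638) = 0.560.
3. Difference detectable with 80% power at 1045: 0.1 x (2.638 + 0.842)/2.802 = 0.124, treating the standard error as unchanged between 0.10 and 0.124.
4. If the 0.05 was one-sided: noncentrality 1.645 + 0.842, about 2.486; critical value 2.394; power Phi(2.486 - 2.394) = 0.537 at 1045, and 0.532 at 1035.

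*Bonferroni does not cover them, and 5.7 sized a score-versus-score difference:* the 80% at 0.05 applies to each single comparison. If the six tests were independent, the chance of at least one false positive would be 1 - 0.95^6 = 0.265. The scores share patients, so this is only a guide.

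*5.7 sized one AUC against a reference value:* the 80% belongs to the validation aim, and the six comparisons have no stated power, whether or not Bonferroni covers them.

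**The case against.** **Part (a) is immaterial.** The gap is 12 patients, about 1% of 1150, and 0.4 points of power. The 9% incidence and the 10% loss are themselves assumptions, and the 9% is a Spanish figure while section 1.9 invites hospitals across Europe. All of this stands. It limits the importance of the slip but does not remove it.

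**Bonferroni may not reach the AUC comparisons.** The sentence in 5.9 follows the t-test, Mann-Whitney and chi-square sentences and comes before the ROC material. It can naturally be read as covering group contrasts over the variables in 5.6. This stands too. A reader might infer that the six comparisons will certainly be tested at 0.0083 and that the study therefore has 56% power. The documents do not support that. The figure needs both that Bonferroni covers these comparisons and that 5.7 sized one score against another, and neither is stated.

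**The size of 1045 might seem to show which difference was meant.** It does not. A two-score calculation contains a correlation that the plan does not give, and a suitable choice of that correlation can produce 1045, so a match is weak evidence. The hypothesis and the first main objective could equally point to a single score against a reference value. For the same reason, any power worked out from assumed AUCs and correlations would describe the assumptions and not this plan.

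**The Mann-Whitney wording may be loose.** The U statistic is closely tied to a single AUC, and the authors may have had that link in mind. As written, though, 5.9 names it as the test between AUCs, and it does not account for pairing.

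**Conclusion.** **(a) Holds, with high confidence and very small effect.** With a 10% loss, 1150 yields 1035 evaluable patients against 1045 needed, and power is about 79.6% if 1045 gives 80%.

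**(b) Holds as an ambiguity, with moderate confidence.** Sections 5.7 and 5.9 together do not tell the reader what power or what error rate applies to the six main-objective comparisons. If Bonferroni covers all six and 5.7 sized a score-versus-score difference with 80% power at two-sided 0.05, power is about 56% per comparison and the detectable difference about 0.124. If Bonferroni does not cover them, that 80% stands for each comparison taken singly, and the error rate across the six is uncontrolled. If 5.7 sized a score against a reference value, the comparisons have no stated power. The documents do not show which case applies, so this is a request for clarification and not a finding that the study is underpowered.

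Separately, the Mann-Whitney U test does not suit AUCs of scores computed on the same patients, whichever reading is right.

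**What to change.** **In 5.7:**

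- Either keep 1150 and state that a 10% loss leaves 1035 evaluable with about 79.6% power, or correct the figure to 1162.
- Say in a phrase whether the 0.1 is between two scores or against a reference value.

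**In 5.9, before the AUC comparisons are run:**

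- State whether Bonferroni covers the six comparisons. If it does, restate in 5.7 the power at 0.0083 from the sponsor's own inputs. If it does not, keep 0.05 and acknowledge the multiplicity.
- In either case, report each AUC difference with a 95% confidence interval from a paired method such as DeLong, in place of the Mann-Whitney U test.

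**Cost:** wording in two sections and a change of AUC comparison method. No extra patients are needed if 1150 is kept, or 12 if it is corrected to 1162; the Bonferroni and method changes need none. If Bonferroni covers the six comparisons, the restated power may be lower than 80%. If it does not, the plan has to accept openly that the error rate across the six is not controlled.

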1.9 Participating Centres

All anaesthesia services and intensive care units of all European hospitals with cardiac surgery services will be invited to participate, most of them belonging to the Spanish group of renal dysfunction in cardiac surgery (GEDRCC2).

2. Background and current status of the issue

Acute *Kidney Injury* (AKI) is a major complication of cardiac surgery and its most severe forms are associated with significant morbidity and mortality^{[1][2]}.

Identification of patients at risk may facilitate early use of management protocols recommended by KDIGO (Kidney Disease: Improving Global Outcomes), such as haemodynamic and volume optimisation, monitoring of renal function and discontinuation or reduction of nephrotoxic drugs^{[3][4]}. The rate associated with cardiac surgery varies according to its different historical definitions, from 0.3% to 29.7%^{[5][6]}. Cases requiring renal replacement therapy (RRT) occur between 1.2%-3.0% in the studied cardiac surgery cohorts and their presence is an independent predictor of mortality.

Because AKI still lacks effective treatments in addition to support and elimination of the cause, early and specific diagnosis is an unmet but critical need for successful and personalised patient management. ^{[8][9][10]}

Creatinine, urea and urine output have been and are the main ways to diagnose and treat renal failure. Other types of biomarkers that seem to be related to risk of postoperative AKI are currently under study. Although more research is needed, they may eventually become predictive diagnostic tools. Several studies have indicated that the urinary level of NGAL^{[11][12]} excreted intraoperatively and after surgery is effective in predicting AKI in both adult and paediatric populations. Similar results have been obtained with other urinary biomarkers, such as the cell cycle arrest biomarkers TIMP-2 and IGFBP7^[11] KIM-1, NAG, IL-18 and L-FAP^[12]. The major limitation of these biomarkers is that they are not easily accessible in all hospitals and clinical settings. Recently Demirjian et al^[13] developed a predictive model in which they observed that perioperative change in serum creatinine and postoperative blood urea nitrogen, serum sodium, potassium, bicarbonate and albumin from the first metabolic panel after cardiac surgery show good predictive value for moderate to severe AKI within 72 hours and 14 days after the surgical procedure.

3. Hypothesis

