4.2 Secondary

- Identify new risk factors for Acute Kidney Injury (AKI)
- Understanding the incidence of AKI after cardiac surgery in Europe
- Validating a model for predicting discharge dialysis after cardiac surgery
- Investigate the performance of these models in specific surgeries: coronary surgery without cardiopulmonary bypass and heart transplantation.
- Assess the performance of other scales and compare them.
- Determine the prevalence and risk factors for Acute Kidney Disease (AKD) (renal injury beyond 7 days, up to 90 days).
- Determine the prevalence and risk factors for new Chronic Kidney Disease (CKD) (follow-up for 120 days or 4 months).
- Determine the prevalence and risk factors for CKD progression, defined by a one-stage progression in patients with pre-existing CKD. Follow-up for 120 days (4 months).

5. Methodology

5.1 Design: descriptive, observational, prospective, multicentre, prospective study.

5.2 Study population: patients undergoing cardiac surgery.

5.3 Ethical aspects: the study has been approved for assessment by the Ethical Committee for Research with Medicines of the Principality of Asturias.

5.4 Inclusion criteria: All patients over 18 years of age undergoing cardiac surgery.

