5.6 Study variables

Hospital

Age

Sex

Male

Female

Race

Asian

Black

Multiracial

White

Weight (kg)

Height(cm)

BMI

Comorbidities

- Hypertension
- Insulin-dependent diabetes
- Non-insulin-dependent diabetes
- Congestive heart failure
- Coronary artery disease
- Triple Vessel coronary artery disease
- Chronic obstructive pulmonary disease
- Poor mobility (musculoskeletal, neurological)
- Chronic kidney disease
- Peripheral vascular disease
- Atrial fibrillation
- Liver disease

NYHA (New York Heart Association Functional Classification)

Left ventricular ejection fraction (LVEF) %

Pulmonary systolic pressure (mmHg)

Unstable angina

Recent miocardial infarction (90 days)

Smoker YES/NO/Ex-smoker

Receives iSGLT2 (dapagliflozin, canagliflozin, empagliflozin...)

Receives GLP1 agonists (liraglutide, semaglutide, dulaglutide...)

Receives calcium antagonists (verapamil, nifedipine, amlodipine...)

Preoperative values

Serum creatinine (mg/dL)

FGe by Cockroft-Gault mL/min/1.73 m²

FGe by EPI CKD ml/min

eGFR by MDRD ml/min/

Serum Albumin (mg/dL)

Serum Urea (mg/dL) or Serum BUN (mg/dL)

Serum sodium (mmol/L)

Serum potassium (mmol/L)

Serum bicarbonate (mmol/L)

Haemoglobin (mg/dL)

Platelets

Bilirubin (mg/dL)

Surgery

On-pump CABG

Off-pump CABG

Valvular

Aortic

Combined (coronary+valvular)

Other, multiple procedures (>2)

Heart transplant

Previous heart surgery

YES/NO

Euroscore II

Classification Surgery

- Emergent
- Urgent
- Elective
- Salvage (pre-operative cardiopulmonary resuscitation)

Catheter to surgery

- Within 24 h
- >24 h this admission
- >24 h previous admission
- No catheter prior to surgery

Pre-operative critical status (IABP, mechanical ventilation, VT, CRP, amines, renal failure)

YES/NO

Endocarditis at the time of surgery

YES/NO

Preoperative cardiogenic shock

YES/NO

Use of IABP prior to surgery

YES/NO

Intraoperative variables

- CPB (cardiopulmonary bypass) time min
- Aorta cross-clamp time (min)
- Vasopressors YES/NO
- Inotropes YES/NO
- Red blood cell transfusion YES/NO

Number of red cell concentrates transfused
Platelet transfusion YES/NO
Fresh Frozen Plasma Transfusion YES/NO
Intraoperative diuresis (ml)
Nadir hemoglobin (lowest intraoperative in mg/dL)
Antibiotic (Gentamicin, Vancomycin, Cefazolin...)

Immediate postoperative values

Time from end of surgery to first analytical panel (hours)
Serum creatinine (mg/dL)
Serum albumin (mg/dL)
Urea (mg/dL) or BUN (mg/dL)
Serum sodium (mmol/L)

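### Section 5.9 never uses the recorded hospital: tests of risk factors that vary by hospital would reject too often, and any incidence or calibration interval computed under independence would be too narrow

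*Combined protocol and SAP*

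**What the plan says.** Section 5.1 describes a "descriptive, observational, prospective, multicentre, prospective study", and section 1.9 states that "All anaesthesia services and intensive care units of all European hospitals with cardiac surgery services will be invited to participate". No number of centres or patients per centre is planned. Hospital is the first variable listed in section 5.6, and section 8 says that the released dataset will carry hospital codes.

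The secondary objectives in section 4.2 include "Understanding the incidence of AKI after cardiac surgery in Europe" and "Identify new risk factors for Acute Kidney Injury (AKI)". The main objective, in section 4.1, is external validation of the score and comparison with other models.

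Section 5.9 is the whole analysis plan. For group comparisons it says "For comparison of means, t-tests for independent data or Mann-Whitney U-tests will be used" and "Chi-square tests shall be used for comparison of proportions". It adds that "Bonferroni correction shall be applied for multiple contrasts". Prediction is assessed by ROC area and the Hosmer-Lemeshow test, with ROC areas compared by Mann-Whitney. No mixed model, GEE, cluster-robust error, stratification by centre or hospital-level resampling is named. Section 5.7 states no design effect, and the limitations in section 5.10 do not mention clustering. Section 5.9 also names no confidence interval for any estimate and no regression model for risk factors.

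**The concern.** In their standard form, all the named tests treat each patient as a separate piece of information. Patients in one hospital share case mix, laboratory practice and perioperative policy, so their AKI outcomes are probably correlated. Two outputs then suffer.

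- **Risk factors.** Some listed candidates plausibly follow local practice: "Antibiotic (Gentamicin, Vancomycin, Cefazolin" and others in section 5.6, transfusion, vasopressors, inotropes, off-pump surgery. The documents do not say that hospital policy sets them; that is a reasonable expectation. If such a factor varies mainly between hospitals, the comparison rests on the number of hospitals more than on the number of patients, and a chi-square or t-test understates its own variance. Bonferroni changes the threshold but does not repair the variance.
- **Incidence and calibration-in-the-large.** Both depend on the overall event rate, whose precision is limited by how much hospitals differ.

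In addition, one pooled Hosmer-Lemeshow p-value cannot show whether predicted risks are right across hospitals, which is a central question in an external validation meant for Europe.

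**Working it through.** **Inputs from the documents.** N = 1045 evaluable patients (1150 after the loss allowance; 1045 × 1.1 = 1149.5) and a 9% incidence of moderate to severe AKI, both from section 5.7. The 9% is a Spanish figure.

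**Inputs assumed.** H = 20 to 60 hospitals and an outcome ICC of 0.01 to 0.05. The documents give neither.

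**The plan's own figure.** The 1045 cannot be reproduced from what is stated, because the reference AUC, the correlation between AUCs and the sidedness are missing. It serves here only as the sample size.

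**Step 1: incidence interval ignoring hospital.** 1.96 × √(0.09 × 0.91 / 1045) = 0.01735, or ±1.74 points (7.3% to 10.7%).

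**Step 2: design effect.** With equal hospitals of size m = 1045/H, DE = 1 + (m − 1) × ICC. The correct half-width is 1.735 × √DE. The true coverage of the naive interval is 2Φ(1.96/√DE) − 1.

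| H | m | ICC | DE | Half-width (points) | Coverage of naive 95% interval | Effective N = 1045/DE |
|---|---|---|---|---|---|---|
| 60 | 17.4 | 0.01 | 1.16 | 1.87 | 93% | 898 |
| 60 | 17.4 | 0.05 | 1.82 | 2.34 | 85% | 574 |
| 20 | 52.25 | 0.01 | 1.51 | 2.13 | 89% | 691 |
| 20 | 52.25 | 0.02 | 2.02 | 2.47 | 83% | 516 |
| 20 | 52.25 | 0.05 | 3.56 | 3.28 | 70% | 293 |

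Unequal hospital sizes make this somewhat worse: beta-binomial simulation over the same ranges gave naive coverage of 65% to 93%.

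**Step 3: chi-square test of a factor with no true effect.** Let the factor have its own ICC, ICC_x: 0 if equally common everywhere, 1 if fixed within hospital. The test's variance is understated by about 1 + (m − 1) × ICC_x × ICC, and its real type I error is about 2[1 − Φ(1.96/√that)]. Simulation with 23 hospitals of 50 patients (4000 replicates) agrees:

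| Factor | Outcome ICC | Variance factor (m = 50) | Type I error, formula | Type I error, simulated |
|---|---|---|---|---|
| Balanced across hospitals (ICC_x = 0) | 0.01 to 0.05 | 1 | 5% | 4% to 5% |
| ICC_x = 0.2 | 0.01 to 0.05 | 1.10 to 1.49 | 6% to 11% | 6% to 10% |
| ICC_x = 0.5 | 0.01 to 0.05 | 1.25 to 2.23 | 8% to 19% | 8% to 18% |
| Fixed by hospital (ICC_x = 1) | 0.01 | 1.49 | 11% | 11% |
| Fixed by hospital | 0.02 | 1.98 | 16% | 16% |
| Fixed by hospital | 0.05 | 3.45 | 29% | 29% |

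Over 20 to 60 hospitals of unequal size, simulated type I error for a factor fixed by hospital was about 8% to 35%. With equal sizes it was 7% to 29%.

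**Step 4: AUC.** Simulations used N = 1045, incidence of 9% to 10%, 20 or 40 unequal hospitals, a hospital random-intercept SD of 0.35 or 0.7, and the same discrimination everywhere. DeLong 95% intervals that ignore hospital covered 93% to 95% for a single AUC and 94% to 96% for a paired difference. In the same runs naive incidence coverage fell to 67% to 90%. Clustering in the event rate alone therefore barely touches AUC inference.

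**Step 5: can hospitals be assessed singly?** Events expected: 0.09 × 1045 ≈ 94, or 94/60 ≈ 1.6 to 94/20 = 4.7 per hospital. That is too few for hospital-level AUCs.

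**The case against.** The strongest reply is that section 5.9 is brief rather than wrong. It specifies no confidence interval, so it rules out no hospital-aware one. Most variables in section 5.6 are patient characteristics (age, sex, comorbidities, laboratory values), for which ordinary tests may hold close to their nominal level. The magnitude rests on an assumed ICC and number of hospitals, and it vanishes as the ICC approaches zero.

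Much of this stands, and it limits the point in four ways.

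- A reader might infer that every p-value and interval in the study is too optimistic. The documents do not support that. No intervals are planned, and a factor balanced across hospitals keeps a type I error of about 4% to 6%.
- A reader might take the phrase on t-tests in section 5.9 as a declaration that hospitals do not matter. There, independent means unpaired groups. The evidence is that no clustering method appears anywhere in the plan.
- A reader might infer that the AUC results behind the main objectives are compromised. Step 4 shows little effect when discrimination is the same in all hospitals. If discrimination differed, AUC intervals would be affected too, and the documents do not say which case applies.
- A reader might infer that 1045 patients are too few because section 5.7 has no design effect. That target concerns an AUC difference, and the design effect calculated here applies to incidence. It does not show that the target is wrong.

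What the reply does not remove is that the tests section 5.9 does name, applied as written to factors that vary by hospital, give wrong error rates if outcomes cluster. Silence on intervals also leaves software defaults, which assume independence, to fill the gap.

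**Conclusion.** The point holds in limited form. Section 5.9 analyses a multicentre cohort only with tests that assume independent patients and leaves the hospital variable unused. The consequences fall on risk factors that vary by hospital and on any incidence or calibration-in-the-large interval computed under independence. With 20 to 60 hospitals and an ICC of 0.01 to 0.05, both assumed, the incidence half-width is about 1.9 to 3.3 points rather than 1.7. Type I error for a factor fixed by hospital is about 8% to 35%; the upper end depends on how unequal the hospitals are. The effect is small at 60 hospitals and ICC 0.01, and already material at 20 hospitals and ICC 0.01 (naive coverage 89%). This is worth correcting before analysis. It does not undermine the main AUC objectives unless discrimination itself varies between hospitals.

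**What to change.** Add one paragraph to section 5.9:

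- Estimate risk-factor associations by regression with a hospital random intercept or cluster-robust standard errors, using a small-sample correction if few hospitals take part. Use the unadjusted t, Mann-Whitney and chi-square tests for description only.
- Report 95% intervals for AKI incidence and calibration from cluster-robust methods or a bootstrap that resamples whole hospitals. For consistency, do the same for AUCs and AUC differences.
- Report the between-hospital spread in calibration-in-the-large by random effects or by country. Do not report AUCs for single small hospitals.
- State the number of hospitals, their sizes and the estimated ICC with the results.

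Hospital is already collected and R is already named, so the cost is a paragraph and modest programming, with no new data or patients. The downside is somewhat wider intervals; if the ICC proves near zero, results barely change. One limit remains: these methods correct the precision of a hospital-driven factor but do not by themselves remove confounding by centre, so such associations still need cautious interpretation.

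### Calibration is assessed only by the Hosmer-Lemeshow test, which shows neither size nor direction of error and usually misses moderate over-prediction at about 94 events

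*Combined protocol and SAP*

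**What the plan says.** Section 4.1 gives as a main objective: "Confirm the usefulness and externally validate the scale". The hypothesis in section 3 is that the score "has a good predictive ability for moderate to severe AKI after cardiac surgery in the European population".

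Section 5.9 sets out how this is judged: "2 measures will be studied, the discrimination ability by means of the area under the ROC curve", followed by "the calibration by means of the Hosmer Lemeshow Test". It does not state the number of risk groups, the degrees of freedom, or whether published risks are used as they stand or the score is refitted first. No other section adds a calibration measure.

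The sample size in section 5.7 rests on an AUC difference: "Taking into account an incidence of moderate severe AKI in Spain of 9% according to previous studies", 1045 evaluable patients, 1150 with losses.

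Section 2 describes the index score as showing "good predictive value for moderate to severe AKI within 72 hours and 14 days after the surgical procedure". Section 5.9 does not say which of the two horizons is validated.

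**The concern.** When a score moves to a new population, baseline risk may differ. Ranking can then survive intact while every predicted risk is too high or too low. The AUC cannot show this, because it depends only on rank order. Calibration has to show it.

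The Hosmer-Lemeshow statistic adds squared deviations over risk groups. Squaring removes the sign, and the p-value mixes the size of the error with the number of events. A significant result does not say what is wrong, and a non-significant one does not show that the score is well calibrated. With few events, a moderately over-predicting score could be reported as calibrated for European patients.

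**Working it through.** **Inputs from the documents.** N = 1045 evaluable and 9% incidence (section 5.7), so 1045 × 0.09 = 94 expected events. The inflation reproduces: 1045 × 1.10 = 1149.5, or 1150. The 1045 itself cannot be confirmed, because no reference AUC or between-model correlation is given. One assumed set (AUC 0.70 against 0.80, correlation 0.3) gives 1048. The point below uses only N and the 9%.

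**Assumptions.** True risk is logit-normal with mean 9% and SD 1.0, 1.3 or 1.6 (AUC about 0.75 to 0.85). There are 10 equal groups by predicted risk. Predictions are not refitted, so df = 10. The level is 5%. Miscalibration is a uniform shift in the odds.

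**Formulas.**
- Hosmer-Lemeshow: Σ (O_g − E_g)² / [E_g(1 − E_g/n_g)] over the groups.
- Direct test: z = (O − E) / √Σp(1 − p).
- 95% CI for O/E: O/E × exp(±1.96 × √[(1 − p)/events]).

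**How often each method detects the error** (10,000 simulated studies per cell; SD 1.0 / 1.3 / 1.6):

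| Predicted odds | Mean predicted risk, % | Hosmer-Lemeshow, % | O/E z-test, % | O/E CI excludes 1, % |
|---|---|---|---|---|
| Correct | 9.0 | 5.3 / 5.8 / 6.5 | 5.1 / 5.3 / 5.1 | not tabulated |
| 1.25 too high | 10.8 / 10.7 / 10.6 | 11.2 / 9.4 / 9.0 | 51.5 / 49.0 / 45.5 | 45.9 / 40.9 / 34.0 |
| 1.35 too high | 11.50 / 11.32 / 11.15 | 24.5 / 21.3 / 19.2 | 78.6 / 75.6 / 72.4 | 74.3 / 68.7 / 60.9 |
| 1.25 too low | 7.5 / 7.5 / 7.6 | 32.3 / 30.0 / 28.0 | 50.6 / 47.7 / 45.5 | 48.1 / 43.1 / 38.3 |

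At 1.35 too high, Hosmer-Lemeshow misses 76-81%, the z-test 21-28% and the CI 26-39%. At 1.25 too high the figures are 89-91%, 48-55% and 54-66%. For under-prediction the gap is much smaller (68-72% against 49-54% for the z-test), so there the small number of events explains much of the loss.

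**What an estimate would show.** With 94 events, √(0.91/94) = 0.098, and exp(±1.96 × 0.098) gives factors of about 0.825 and 1.213.
- 1.35 too high: 0.09/0.1150 = 0.78 (0.65-0.95); 0.09/0.1132 = 0.80 (0.66-0.96); 0.09/0.1115 = 0.81 (0.67-0.98). At its expected value O/E has a CI below 1, although Hosmer-Lemeshow is non-significant in about 8 of 10 studies.
- 1.25 too high: 0.83 (0.69-1.01) to 0.85 (0.70-1.03). The CI includes 1 but shows the plausible range.

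**Second check, by true O/E** (separate simulation, 10 df). At O/E 0.80, Hosmer-Lemeshow has power of 18-22% and a calibration-intercept test 68-77%. At 0.75 the figures are 40-48% and 91-96%; at 0.70, 71-80% and about 99%. If the score is refitted in the new data before testing, Hosmer-Lemeshow rejects in only about 4-6%, whatever the over-prediction.

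**The case against.** **Large errors are caught.** This stands. At odds 1.5 too high (O/E 0.72-0.75) Hosmer-Lemeshow detects 46-58%, and at 1.75 (O/E 0.64-0.68) 90-95%. The criticism applies to O/E of about 0.80 or nearer 1.

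**Software often uses 8 df, which rejects more often.** True, and the plan does not state the df. With 8 df the test still misses 57-67% at odds 1.35 too high, and it rejects a perfectly calibrated score in 11-13% of studies. Part of the apparent gain is therefore false alarm.

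**A uniform shift favours O/E.** Also true: a one-parameter test suits that error, whereas Hosmer-Lemeshow is an omnibus test. O/E can sit near 1 when the slope is wrong, so O/E alone would not be enough. This is why the slope and the plot are needed as well.

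**Observed and expected counts per group are by-products of the test.** They are, and size and direction could be read from them. The plan does not commit to reporting them, and a choice made after the results are seen is not pre-specified. This makes the remedy easy and leaves the gap in place.

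**Conclusion.** The concern holds. The absence of size and direction needs no assumption. It follows from the test and from section 5.9 naming no other calibration measure.

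The detection figures rest on assumed risk spread, 10 groups, 10 df and a uniform shift in odds. Across AUC 0.75-0.85 the conclusion is stable: over-prediction at O/E of about 0.78-0.85 is missed in roughly 76-91% of studies. It should not be extended to gross over-prediction, and for under-prediction the disadvantage of the test is smaller.

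The study remains feasible and the AUC analysis is unaffected. The weakness is that half of the stated assessment of predictive ability would end in a p-value. The unstated horizon is a minor clarification: the outcome can be inferred as moderate to severe AKI, but the time window cannot.

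**What to change.** In section 5.9:
- Make the calibration measures the O/E ratio (or calibration intercept) and the calibration slope, each with a 95% CI, plus a calibration plot.
- Compute them on the published predictions without refitting, wherever a published equation gives probabilities.
- Keep Hosmer-Lemeshow as supplementary, with the number of groups stated and df equal to that number for unrefitted predictions.
- Add one line giving each model's target outcome and horizon (72 hours or 14 days for the index score), and assess each model against its own target.

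**Cost.** A few lines of text and R code. No new data are needed: section 5.6 already collects serial creatinine and the day of each AKI stage and of renal replacement therapy (RRT).

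**Downside to state.** Precision is modest. For a well-calibrated score with 94 events, the expected 95% CI for O/E is about 0.82-1.21. For the slope, standard errors of 0.125 (SD 1.0) and 0.097 (SD 1.6) give 0.75-1.25 and 0.81-1.19. An RRT outcome would be far less precise. Section 2 reports that "Cases requiring renal replacement therapy (RRT) occur between 1.2%-3.0% in the studied cardiac surgery cohorts". If those rates applied here, which is an assumption, 1.2% gives 12.5 events and an O/E interval of about 0.58-1.73, and 3.0% gives 31.4 events and about 0.71-1.41.
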